2.3.1.1. Schematic study design

The study design is schematically presented in Figure 2.1, depicting Phase I, Phase II and their interval. Figure 2.2 presents the timeline of the study, beginning month 19th (M19) and expected to be completed by month 41st (M41).

Group A (personalized NUTRISHIELD Full evaluation dietary plan) of biomarkers. Data dietary habits analyses and other assessments Group B (common dietary instructions) Randomisation 6 mo 4 mo 9 mo Phase I: Phase II: Observational Intervention

Figure 2.1: Study I design

Figure 2.2: Study I timeline

		Phase I								Phase II													
Recruitment-Phase I	M19	M20	M21	M22																			
Pause between Phase I & II					M23	M24	M25	M26	M27	M28	M29	M30	M31										
Phase II- Intervention (6 mo + 3 mo)														M32	M33	M34	M35	M36	M37	M38	M39	M40	
Phase II- control (6 mo + 3 mo)														M32	M33	M34	M35	M36	M37	M38	M39	M40	
Data analysis																				M38	M39	M40	M

2.3.2. Participants

Participants will be recruited at the San Raffaele Hospital (OSR). All visits and blood and urine sample collection will be held at the hospital. Fecal sample collection (for microbiome analysis) will be performed at home.

Inclusion criteria

Children with obesity and/or diabetes, aged 8-18 years visiting hospital on an outpatient basis.

Exclusion criteria:

- Children with any acute or chronic disease (tumor, infection, others), gastrointestinal diseases, cardiovascular disease, chronic renal disease, diseases of the parathyroid, diseases necessitating regular phlebotomies, and other chronic diseases which could affect the results of the study
- Use of medicine which could affect the results of the study, such as systemic glucocorticoids,
 lipid-lowering or anti-hypertensive drugs
- Recent weight loss or weight gain (> 3 kg), within the previous 3 months of the beginning of the study
- o Transfusion of blood in the last three months before Study Phase I
- Use of dietary supplements, including multivitamins, fish oil capsules, minerals, and trace elements (three months before and during the entire study period)
- Inability (physically or psychologically) to comply with the procedures required by the protocol.

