2.3.1. Study design

The details of the study design where optimized following discussions with the NUTRISHIELD partners (during the meeting held on Athens 9-10/4/2019, mails exchange and teleconferences) to better serve the project purposes. Small deviations from the Description of Action were decided regarding the study design related to the groups and the timeline without altering the overall goals of the study.

The proposed study is a two-arm, parallel, randomized controlled study, with a dietary intervention for children (8-18 year old) with obesity or diabetes (type I or II). It will be carried out in Ospedale San Raffaele hospital between M19 to M41. The study protocol will be approved by the Ethics Committee, and written informed consent will be obtained from all caregivers and/or participants. All procedures regarding volunteers' recruitment and participation, data security and handling will be in absolute accordance with the principles set under Work Package (WP) 9, concerning Ethical Requirements, and more specifically stated on Tasks 7.1 and 7.2 and D 7.2.

H2020 Contract No 818110

The study will be divided into two phases:

- 1. **Phase I**: the **Observational** phase, lasting at least four months. During this period children will be recruited and their diet and biomarkers will be assessed once, as described below. At the end of the observational phase and recruitment period, the study will pause for nine months (from M23 to M31) in order to perform machine learning analyses, feed the platform and train the personalized nutritional algorithm with the results from the preceding assessments of the observational phase.
- 2. **Phase II**: the **Intervention** phase, lasting six months. During this period children recruited in the study will be randomly allocated to one of the two groups:
 - Group A (Intervention) will receive a NUTRISHIELD-derived personalized diet
 - **Group B (Control)** will follow the standard European dietary guidelines for obesity/diabetes, i.e. the usual care/control diet.

Diet as well as biomarkers and clinical data will be evaluated at the beginning and at the end of the intervention phase.

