2.3.4.2. Measurements

All children will be thoroughly evaluated at baseline (before the intervention begins) and post-intervention (after the end of intervention). Evaluation includes sociodemographic profile (baseline only), dietary and lifestyle habits, anthropometric measurements, microbiome, metabolome and genotype (baseline only) profiling. Sociodemographic assessment and genotype profiling will be performed only in the observational phase and will not be repeated during the intervention Phase I.

o Sociodemographic information

Sociodemographic information will be collected from all children at baseline [21, 22], as described above.

Dietary assessment

At baseline and post-intervention the most valid method as evaluated in study phase I will be used, as described above (2.3.3 Study Phase I, Measurements: Dietary assessment). Two methods of dietary assessment will be compared during Phase I, namely a 4-day food record (supported by a mobile app for food pictures uploading) and an extensive semi quantitative food frequency questionnaire (FFQ), primarily aiming at evaluating the validity of the FFQ against the 4-day food record.

[figure not shown]
Moreover, for the evaluation of adherence to the Mediterranean Diet, the KIDMED score will be used [24], as described above.

o Other lifestyle behaviors assessment

Physical activity level, sleep duration and smoking habits will be assessed as described above. Furthermore, children will report whether they have a TV set in their room, the intake of dietary supplements and whether they are medically diagnosed with dietary allergies or other diseases as described in the former section.

Anthropometric assessment

Children's weight will be measured on leveled platform scale to the nearest 0.5 kg and height on a wall-mounted stadiometer to the nearest 0.5 cm. BMI (kg/m²) will be calculated by dividing the weight in kilograms by the height in meters squared.

Medical history assessment

Children's medical history will be recorded by asking all the chronic conditions that they may have.

Genotype characterisation

A buccal swap sample will be collected from all children at baseline. In specific, standard buccal swab kits will be used to gather DNA sample for sequencing, as described in Deliverable 3.1.

Metabolome characterisation

For the characterisation of the children's metabolic profile, urine and blood samples will be collected as described in Deliverables 2.2 and 3.1.

Microbiome assessment

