2.3.5.2. Randomisation

The randomisation, either to Group A or Group B, will be performed by an 2X2 block randomization on the basis of age of children (i.e., ≤12 and >12 years old, 1:1 ratio) and sex of children (1:1 ratio). The random allocation sequence (i.e., sequentially numbered containers), will be developed using STATA v15.0 software and relevant commands. Specifically, stream random-number generators will be used. One seed value will set and then using the software and particularly a stream version of the 64-bit Mersenne Twister, Stata's default pseudorandom-number generator, a random sequence of binary numbers will be created that allocate children to each study's Group.

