Weight and height of mothers of the PT-OMM, PT-DHM, and FT-OMM will be measured. Weight will be measured on a levelled platform scale to the nearest 0.5 kg and height on wall-mounted stadiometer, to the nearest 0.5 cm. Body Mass Index (BMI) (kg/m²) will be calculated by dividing the weight in kilograms by the height in meters squared.

All infants will be evaluated regarding their growth by measuring weight, length and cranial perimeter upon every visit at the hospital. Weight and recumbent length will be measured on an electronic baby scale and on a neonatometer scale, to the nearest 0.5 kg and 0.5 cm respectively and cranial perimeter will be measured using a flexible inch tape to the nearest 0.5 cm.

Medical history assessment

At observational phase PT-OMM, PT-DHM and FT-OMM mothers' medical history, i.e. all the chronic conditions that they may have as well as the use of medicines, will be recorded.

Genotype characterisation

A buccal swap sample will be collected from mothers of PT-OMM, PT-DHM and FT-OMM at baseline. In specific, standard buccal swab kits will be used to gather DNA sample. Furthermore, umbilical cord

blood will be extracted from PT-OMM, PT-DHM, and FT-OMM newborns. The detailed protocol is described in Deliverable 3.1.

Metabolomecharacterisation

For the characterization of metabolic profile urine samples will be collected from mothers of PT-OMM, PT-DHM and FT-OMM and their infants, as described in Deliverables 2.2 and 3.1.

Microbiome assessment

Fecal samples from all mothers and their infants will be collected for studying the microbiome. The protocol followed is described in Deliverable 2.1.

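### Study I does not say whether glucose-lowering treatment is an excluded medicine, and does not state that medicine use is recorded, although four of its six primary end points are glycaemic

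*Protocol*

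**What the plan says.** Protocol section 2.3.1 describes a randomised dietary trial in "children (8-18 year old) with obesity or diabetes (type I or II"). The inclusion criterion in 2.3.2 reads "Children with obesity and/or diabetes, aged 8-18 years visiting hospital on an outpatient basis" and sets no condition on treatment. Section 2.3.4.3 confirms that diabetic children are evaluated in Phase II, tying HOMA-IR to type II and c-peptide to type I.

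The exclusion list in 2.3.2 contains "Use of medicine which could affect the results of the study, such as systemic glucocorticoids", and continues with "lipid-lowering or anti-hypertensive drugs". The list is open-ended. It neither names nor exempts insulin or other glucose-lowering drugs.

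Section 2.3.6 names weight, BMI, blood glucose, insulin, A1C and HOMA-IR as primary end points, with no restriction by diabetes type.

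On data collection, 2.3.4.2 says "Children's medical history will be recorded by asking all the chronic conditions that they may have", and 2.3.3.1 says the same for Phase I. Dietary supplements are listed for recording and medicines are not. For the mothers in Study II, section 3.3.3.1 is wider: "all the chronic conditions that they may have as well as the use of medicines, will be recorded".

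Randomisation (2.3.5.2) is stratified "on the basis of age of children (i.e., ≤12 and >12 years old, 1:1 ratio) and sex of children (1:1 ratio").

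**The concern.** The medicine exclusion turns on whether a drug could affect the results, and glucose-lowering treatment acts directly on end points that 2.3.6 calls primary. Staff at screening have two defensible readings, and they lead to different trials. Under one, a population named in the design section largely disappears. Under the other, treatment that acts on four of the six primary end points is present, may be altered over six months, and leaves no trace in the data described here.

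The second case matters because randomisation balances treatment at the start, in expectation, but not what happens afterwards. If one arm's treatment is altered more often, part of any A1C or glucose difference may reflect that, or a real dietary benefit may be hidden by it (for example, the same A1C on less insulin). Doses that were never collected cannot be recovered by any later analysis. Objective (a) in 2.2 compares the diets on health indices that include biochemical markers, so the interpretation of that comparison is at stake.

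**Working it through.** **1. The passages side by side.**

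| Question | Study I text | Consequence |
|---|---|---|
| Who is included? | Obesity and/or diabetes, type I or II (2.3.1, 2.3.2) | Treated diabetic children qualify |
| Which medicines exclude? | Any that could affect the results; three example classes, none glucose-lowering (2.3.2) | Literal reading: treated children excluded. Reading by example: treatment allowed |
| What is primary? | Glucose, insulin, A1C, HOMA-IR, weight, BMI (2.3.6) | Glucose-lowering treatment acts on the first four |
| What is recorded? | Chronic conditions (2.3.3.1, 2.3.4.2) | Drug and dose not stated; contrast Study II, 3.3.3.1 |

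The two consequences in the second row are alternatives and should not be added together. Under the literal reading, the 80 places could still be filled with children not on such treatment, so the first loss is of population, not necessarily of power.

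**2. The plan's own figure.** Section 2.3.5.1 gives a difference of 15, an SD of 20 and 40 children per group. The standardised difference is 15/20 = 0.75. Power = Φ(0.75 × √(40/2) − 1.96) = Φ(3.354 − 1.960) = Φ(1.394) = 91.8% (91.2% with the t distribution). The stated minimum of 90% is reproduced. The point does not rest on this figure; it supplies the 0.75 SD yardstick.

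**3. An illustration of size.** The protocol gives no share of diabetic or treated children and no treatment effect, so every input here is an assumption:
- share of the 80 children with diabetes, p = 0.30 to 0.50 (24 to 40 children);
- excess share of those diabetic children whose therapy changes in one arm, g = 0.10 to 0.30;
- A1C shift per change, e = 0.5 to 1.0 points;
- SD of A1C = 1.0 point.

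Shift between arms = p × g × e / SD.
- Low end: 0.30 × 0.10 × 0.5 / 1.0 = 0.015 SD; 0.015/0.75 = 2% of the target.
- High end: 0.50 × 0.30 × 1.0 / 1.0 = 0.15 SD; 0.15/0.75 = 20% of the target.

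**4. What the high end would do.** With 40 per arm the shift enters the test as 0.15 × √20 = 0.671.
- No direct dietary effect: rejection rate = Φ(0.671 − 1.96) + Φ(−0.671 − 1.96) = 0.099 + 0.004 = 10.3%, against a nominal 5%.
- True effect of 0.75 SD, partly masked: Φ(0.60 × √20 − 1.96) = Φ(0.723) = 76.5%, against 91.8%.

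**5. Insulin and HOMA-IR.** Both are primary in 2.3.6. In a child who may be receiving insulin, a change in the measured value could reflect treatment as well as diet. Section 2.3.4.3 links HOMA-IR to type II only, but 2.3.6 does not carry that limit over and restricts serum insulin in neither type.

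**The case against.** **Barring treated children is probably not intended.** The inclusion criteria admit diabetes expressly, and the listed examples treat other conditions. The neighbouring exclusion of chronic disease, read equally literally, would remove diabetic children too. This stands: it is a drafting ambiguity, and a reader should not infer that the sponsor means to exclude them. The text still has to say so.

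**The trial is randomised and physicians are blind.** A reader might infer that a glycaemic difference could not be attributed to the diet at all. The documents do not support that. Treatment at entry is balanced in expectation, and a treatment change brought about by the assigned diet is part of the effect of assignment. Section 2.3.5.3 also blinds physicians and biostatisticians, which makes treatment changes that follow the arm less likely. The protection is partial: the wording ties the blinded staff to baseline analysis and interpretation, dietitians are not blind, and families are not listed as blind.

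**Medicines may be recorded elsewhere.** Applying the exclusion requires asking about medicines at screening. Section 2.3.1 mentions clinical data at the start and end of Phase II, and 2.3.4.3 defers partly to Deliverable 2.8, which is not at hand. The appendix dictionary has no medicine item, but it is sociodemographic and has none for Study II either, so its silence proves nothing. What stands is only that this protocol does not state that drug and dose are recorded.

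**A larger size is tempting.** Applying the 10-30 point gap to all children, not only the diabetic ones, gives up to 0.30 × 1.0 = 0.30 SD, or 40% of the target. But 30% of 40 children is 12. With 24 diabetic children, about 12 per arm, every one in one arm would have to change therapy and none in the other. The documents give no ground for that.

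**Stratification.** A reader might infer that diabetes status must replace sex as a factor. Chance imbalance is already covered by the test's error rate, diabetes status is obtainable from the recorded history, and 2.3.6 allows adjustment based on the baseline analyses.

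**Conclusion.** The point holds in limited form. The inclusion criteria, the medicine exclusion and the primary end points do not fit together as written, and this protocol does not state that medicine use is recorded in Study I. If glucose-lowering treatment is allowed, a difference in glucose or A1C between arms can be credited to assignment but not separated from treatment changes after randomisation, and serum insulin and HOMA-IR are hard to interpret.

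The likely size is modest: about 0.015 to 0.15 SD, or 2% to 20% of the planned 0.75 SD. That range rests wholly on the assumed shares, the A1C shift and the SD, and it applies to A1C. Weight and BMI lie largely outside the argument. The reason to act before Phase II is that the missing information could not be recovered later and costs little to collect.

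**What to change.** 1. Reconcile 2.3.1, 2.3.2 and 2.3.6 so that the protocol states whether glucose-lowering treatment is permitted. This review takes no position on which rule is right, or on how treatment should be managed.
2. If it is permitted, add to 2.3.4.2 a record of drug and dose, including insulin, at Phase II baseline, at the monthly visits already scheduled in 2.3.4.1, and at the end of the intervention.
3. Report treatment changes by arm beside the glycaemic end points, and pre-specify a sensitivity analysis that accounts for them.
4. Keep age and sex as stratification factors, and adjust for diabetes status, taken from the medical history, in the analysis.

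The cost is a wording amendment, one extra form item at existing visits and a little more analysis.

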Fecal samples from all children will be collected repeatedly for microbiome analyses. The protocol is described in Deliverable 2.1.

2.3.4.3. *Outcomes*

To evaluate the effectiveness of the intensive personalized dietary intervention changes in dietary, lifestyle, growth-related and metabolic factors will be assessed, as described below and in Deliverable 2.8.

Dietary factors

Changes in dietary factors are expected after the personalized intervention. In specific, energy intake, the composition of the diet in macro-nutrients, especially of saturated and trans-fatty acid intake [31] as well as specific micro-nutrients, such as vitamin D and iron [32, 33] are expected to improve. What is more, consumption of specific food groups, such as fruits and vegetables [34-37] and dairy products [37-40] is expected to change. Finally, adherence to the Mediterranean Diet is expected to increase [41].

Other lifestyle factors

Levels of children's physical activity after the implementation of the platform-derived personalised diet are expected to increase [42-44].

Growth related factors

Regarding children's weight, height and BMI status is expected to change and will be compared to the available growth charts proposed by the World Health Organization [45].

Clinical outcomes

To test the effect of the personalised diet intervention on clinical diabetes we will evaluate possible improvement in the metabolic profile of children such as blood glucose, insulin, A1C, HOMA-IR (Type II diabetes) and c-peptide (Type I diabetes) [46, 47]. In addition, cardiometabolic risk factors such as total cholesterol, LDL cholesterol, HDL cholesterol, LDL/HDL cholesterol ratio and triglycerides will be also assessed [48].

Microbiome-related factors

In the post intervention phase, changes in the gut microbiome related to dietary modifications are expected to occur [49]. We also expect to detect alteration of the metabolome profile at the systemic level (blood and urine), such as changes in the quantity of colonic short chain fatty acid [50].

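### Study I's supplement exclusion runs past randomisation, and the protocol does not say that a child who starts a supplement in Phase II stays in follow-up and in the assigned group

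*Protocol*

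**What the plan says.** The Study I exclusion criteria (Protocol 2.3.2) include "Use of dietary supplements, including multivitamins, fish oil capsules, minerals, and trace elements (three months before and during the entire study period"). A neighbouring criterion has a window that closes before the study starts: "Transfusion of blood in the last three months before Study Phase I". The weight-change criterion is likewise tied to the beginning of the study.

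Randomisation comes late. After the observational phase and the nine-month pause, "children recruited in the study will be randomly allocated to one of the two groups" (2.3.1), at the start of "the Intervention phase, lasting six months". The timeline in 2.3.1.1 puts the start of Phase II at M32.

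For Phase II, section 2.3.4.2 says: "All children will be thoroughly evaluated at baseline (before the intervention begins) and post-intervention (after the end of intervention"). It also says that "children will report whether they have a TV set in their room, the intake of dietary supplements". Section 2.3.4.3 names vitamin D and iron among the dietary outcomes: "specific micro-nutrients, such as vitamin D and iron [32, 33] are expected to improve".

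**The concern.** An eligibility criterion should use only what is known at allocation. This one also covers behaviour during the six months after it. A site that applies the criterion as written could stop following a randomised child who begins a supplement; a site that follows 2.3.4.2 would keep the child and record the use. The protocol supports both and does not choose.

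The choice matters because supplement use after randomisation may be affected by the arm. Under 2.3.4.1, Group A receives successive plans built on genome, diet and biochemical markers, while Group B receives standard advice. Section 2.3.5.3 states that the counselling dietitians cannot be blinded. Detection could differ too: 2.3.4.1 attaches evaluations to Group A's monthly visits but mentions only visits for Group B. If children are removed for an event that treatment can influence, the remaining groups are no longer those that were randomised. A larger sample does not repair that. Outcomes that a site never collects also cannot be recovered at the analysis stage.

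**Working it through.** **1. Which part of the window matters.** Set against the 2.3.1.1 timeline, the window has three parts.
- Phase I (M19-M22): before allocation. Exclusion here affects who is enrolled, not the randomised comparison.
- Pause (M23-M31): also before allocation, so the same applies.
- Phase II (from M32): after allocation. Only here can exclusion bias the comparison.

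**2. The plan's own power.** Inputs from 2.3.5.1: 40 per group, difference 15, SD 20, two-sided 5%. The standardised difference is d = 15/20 = 0.75. For the two-sample t-test with n per group, the noncentrality is d × √(n/2) on 2n − 2 degrees of freedom. At n = 40 it is 0.75 × √20 = 3.354 on 78 df, giving power 91.2% (91.8% by the normal approximation). The stated figure of at least 90% is reproduced.

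**3. Power if children are removed.** The documents give no rate of supplement use, and 2.3.5.1 mentions no allowance for losses. The removal rates below are assumptions.

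| Removed per arm (assumed) | n per arm | Power at 0.75 SD |
|---|---|---|
| none | 40 | 91.2% |
| one child | 39 | 90.5% |
| 5% | 38 | 89.7% |
| 10% | 36 | 88.1% |
| 20% | 32 | 84.0% |

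The margin above 90% is therefore one child per arm. If only one arm loses children, the loss of power is smaller: 32 against 40 gives 87.7%.

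**4. Bias if removal is one-sided.** Let a share f of one arm be removed, and let those children differ by g SD from the children retained. The full-arm mean is (1 − f) × retained mean + f × removed mean, so the retained mean is off by f × g. Both f and g are assumptions.

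| f | g = 0.25 SD | g = 0.5 SD | g = 1.0 SD |
|---|---|---|---|
| 10% | 0.025 | 0.05 | 0.10 |
| 20% | 0.05 | 0.10 | 0.20 |

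At g = 0.5 the bias is 0.05/0.75 = 7% to 0.10/0.75 = 13% of the planned difference. Its sign follows that of g. If both arms lose children, the net bias is f × g in one arm minus f × g in the other, which is zero when the two are equal.

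Steps 3 and 4 are separate scenarios, loss in both arms and loss in one, and should not be added together.

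**The case against.** The strongest reply is that no section says a randomised child who starts a supplement is withdrawn or left out of the analysis. The Phase II text leans towards keeping the child, since all children are evaluated at the end and supplement intake is asked about. On that view the phrase is loose drafting of a restriction on use during the trial, and deviations and analysis sets are matters for a statistical analysis plan.

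Much of this stands. A reader might infer that the trial will drop supplement users, but the documents do not state it; it is only the literal consequence of listing the rule as an exclusion criterion. A reader might also infer that removal would favour a particular arm. Nothing supports a direction: starters could be the less healthy children or those from more health-conscious families. Nor do the documents show that starting differs by arm, or that it relates to the primary end points in 2.3.6 (weight, BMI and the glycaemic measures). That families know their allocation is plausible, but 2.3.5.3 does not mention them.

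Two things survive. The window of an eligibility criterion is the protocol's own wording, and it can determine whether a site continues follow-up, which no later analysis plan can undo. And 2.3.2 and 2.3.4.2 give different signals about the same child.

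**Conclusion.** The point holds as a defect of wording in the randomised part of Study I. Sections 2.3.2 and 2.3.4.2 need to be reconciled, because the first makes behaviour after randomisation a ground for exclusion and neither says what happens to the child.

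The effect on the results cannot be determined from the documents. Under assumed removal of 10-20% per arm, power at 0.75 SD falls from 91% to 88-84%. Under assumed removal of 10-20% from one arm, with a 0.5 SD difference between removed and retained children, bias is 0.05-0.10 SD in either direction. These figures show what is at risk if the criterion is applied literally; they do not forecast what will happen. The stronger conclusion, that the trial will lose randomised children and so favour one arm, is not supported.

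**What to change.** In 2.3.2, apply the supplement criterion as an eligibility rule only up to the Phase II baseline, that is, up to randomisation. In 2.3.4.2, state that use after randomisation is recorded as a protocol deviation or intercurrent event, and that the child stays in follow-up and is analysed in the assigned group. Add a sensitivity analysis of the micronutrient outcomes that takes account of children who took supplements.

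Whether supplement use is restricted during the intervention is for the sponsor to decide; the change does not depend on it.

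The cost is one or two sentences and one extra analysis. The intake question already exists in 2.3.4.2, so no new data collection is needed. The downside is some supplement-related noise in the micronutrient outcomes, which the sensitivity analysis is meant to gauge. With every randomised child kept and followed, this source of bias does not arise and power stays at 91.2%.
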